patients (7 men and 8 women, mean age 62 years) who underwent OctreoScan with SPECT/CT of the chest for a clinical indication between the periods of April and November of 2013 at the University of Washington in Seattle. Most common clinical indication was detection of local and/or metastatic neuroendocrine tumors. Patients were injected with ~ 6 mCi of OctreoScan, and SPECT/CT of the chest was acquired 24 hr post-injection. OctreoScan uptake was semiquantitatively calculated using a target to blood pool ratio approach. Figure 2 depicts fused SPECT/CT images of how this was performed. Circular region of interests (ROI) of ~20 mm diameter were applied to left ventricular (LV) cavity blood pool (used as background, 2A and 2D), LV anterior (2B), inferior (2C), lateral wall (2E) and septum (2F), as well as the lungs (not shown), liver (2G), spleen (2G) and kidneys (2H). Results: Visually, the myocardium exhibited indistinguishable activity compared to the LV blood pool. However, there was significant LV regional differences in the uptake ratio/index as shown in **Table 1**. The inferior wall and septum showed higher (above blood pool) and the lateral and anterior walls lower (below blood pool) uptake ratios. This is most likely due to scatter emitted from the liver and spleen (Fig 2G) into the inferior wall (Fig 2C) and, to a lesser extent, the inferior portion of the septum. Likewise, identification of the septal wall (Fig 2F) was difficult given the lack of enough contrast definition on SPECT and CT images, for which an anatomical assumption was made, which makes ROI-based estimates less accurate at this location. These data demonstrated that under baseline conditions. OctreoScan uptake in the heart is indistinguishable from LV blood pool (~ 0.94 ± 0.17). These findings provide solid empirical basis for the work proposed in this project; the hypotheses are mechanistically plausible, clinically important, and testable.

d. Differences between OctreoScan and DOTATATE

There are important biological, technical, and practical differences between these radiopharmaceuticals that deserve a brief mention. Like indium-111 pentetrotide (Octreoscan®), 68-gallium dotatate has similar affinity for the same group of somatostatin receptors in inflammatory leukocytes (preferentially somatostatin receptor 2). The availability of 68-gallium dotatate provides several advantages, which are highly beneficial to the patients in this pilot study, including:

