- a. higher contrast and spatial resolution of PET/CT for detection of small lesions, which we think will result in improved sensitivity as compared to indium-111 pentetrotide SPECT;
- b. a nearly 75% reduction in the whole body effective radiation dose to patients from a single administration of gallium-68 dotatate (from 16.4 mSv for Octreoscan to 4.3 with Dotatate);
- c. convenience for patients and practical to perform. The entire gallium-68 dotatate PET imaging procedure takes ~2 hours in a single visit, compared to ~24 hours over 2 visits for octreoscan imaging.

II. SPECIFIC AIMS

Aim 1

To investigate if patients with clinically suspected cardiac sarcoidosis exhibit a myocardial OctreoScan or DOTATATE signal high enough (heart-to-blood pool ratio ≥ 2.0) to be visually detected compared to a control group of individuals (expected heart-to-blood pool ratio of ~ 1.0).

Sub-Aim1

To evaluate whether 4-hour (early) compared to 24-hour (delayed) post-OctreoScan injection imaging yields similar lesion detection performance.

Sub-Aim2

To correlate localization and number of increased radiotracer foci between FDG-PET and OctreoScan or between FDG-PET and DOTATATE studies.

Sub-Aim3

To explore the effect of treatment on DOTATATE activity in the heart on follow-up scans

III. SUBJECT SELECTION

We will enroll 30 adult subjects meeting the following inclusion/exclusion criteria.

a. Inclusion Criteria for initial study

- Individuals aged 18 or older

- Documentation of biopsy-proven sarcoidosis OR patients with typical findings on FDG PET and MRI without previous biopsy.

- Clinical suspicion of cardiac involvement defined as the presence of any of the following: high-degree A-V nodal block, complete bundle branch block, reduced left or right ventricular systolic function, any cardiac arrhythmia, and/or unexplained chest pain, dyspnea or syncope

- PET/CT imaging demonstrating abnormal myocardial FDG uptake consistent with active inflammatory myocardium.

b. Exclusion Criteria for initial study

-Initiation of steroids or any other immunosuppressive medication(s) following the completion of FDG-PET, as these medications, in theory, may subsequently suppress OctreoScan or DOTATATE uptake in the heart.

- Patients with history of neuroendocrine tumors (specially insulinomas)
- Patients taking the medication Octreotide
- Patients on total parenteral nutrition (TPN)
- Women who are pregnant or breastfeeding

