Enrolled patients will be prospectively imaged after injection of either the radiotracer Indium-111 Penteotride (OctreoScan) or DOTATATE. We expect imaging 10 patients with OctreoScan and 20 patients with DOTATATE. No one will receive both radiotracer injections.

Patients will be scheduled for imaging Tuesday through Friday (no Mondays), since the dose of OctreoScan and DOTATATE must be requested by noon for next day delivery. Subjects will be advised to remain well hydrated prior to and for at least one day after tracer injection, this to reduce radiation exposure.

Women may participate in this study only if they are certain they are not pregnant. If the subject is a woman of childbearing age, a pregnancy test will be performed before OctreoScan or DOTATATE injection unless she has a history of total hysterectomy, is post-menopausal for more than 2 years or post-tubal ligation for more than 1 year.

OctreoScan Protocol

Visit 1 (Screening)

- Review the study with the subject and obtain written informed consent and HIPAA authorization.
- Assign the subject a unique study number.
- Record demographics data.
- Record medical history, including a history of biopsy-proven systemic sarcoidosis, diagnosis date, and prior treatments.
- Record concomitant medications.
- Schedule subject for Visit 2.

Visit 2 (Study Day 1)

- Subject arrives to the Nuclear Medicine Department.
- Concomitant medications review.
- Perform abbreviated physical examination.
- Perform and record vital signs.
- Place a peripheral intravenous (IV) line.
- Perform STAT quantitative serum hCG testing prior to each administration of Octreoscan
- Administer OctreoScan IV.
- Observe patient for 30 minutes post OctreoScan injection.
- Patient is to have a break and return to the Nuclear Medicine Department in 4 hours.
- Perform first set of images (~90 minutes)
- Subject can leave the Nuclear Medicine Department

[figure not shown]
Visit 3 (Study Day 2)

- Subject returns to the Nuclear Medicine Department 24 hours after OctreoScan injection
- Record any Adverse Experiences.
- Perform second set of images (~90 minutes).
- Subject has completed the study protocol at this point.

Follow Up

• All patients will be contacted by telephone at approximately 36-48 hours following the last scan for AE monitoring.

Figure 3. Example of Study Visits for OctreoScan Protocol

Study Day 1 (Approximately 6 hours)

Study Day 2 (Approximately 2 hours)

24 hours post	Whole Body	SPECT/CT	

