DOTATATE will be given intravenously at the dose of 4.0 mCi (148 MBq). They will then be observed for 60 minutes post DOTATATE injection at the nuclear medicine lab.

Cardiac acquisition: Individuals will be positioned with the help of a CT topogram (grid over the heart, level of the carina), and a low-dose CT scan (120 kVp, 20 - 30 mA) will be acquired for attenuation correction of PET emission data to cover the entire chest. This will be followed by a 20-minute ECG-gated 3-D PET acquisition of the chest and myocardium.

Imaging Processing:

All PET images will be reconstructed with attenuation correction (Matrix 128x128, OSEM, subsets 28, iteration 2, post filter 6.0 mm), and processed and reviewed using the vendor-supplied HERMES software package.

d. Data to be collected and when the data is to be collected

Visit 1. We will collect demographics data, medical history, prior treatments, and concomitant medications, as well as confirm a negative STAT quantitative serum hCG testing prior to the administration of Octreoscan or DOTATATE.

After visit 3 for OctreoScan or after visit 2 for DOTATATE we will analyze and interpret the images as following:

Image Interpretation for OctreoScan:

OctreoScan uptake in the heart will be assessed both qualitative and semi-quantitatively.

1. Qualitative Assessment of OctreoScan cardiac uptake: Two board-certified nuclear medicine physicians will review the early and delayed whole body planar and SPECT/CT images independently of each other and grade each image set based on OctreoScan uptake in the heart as: 1) negative, 2) borderline positive or 3) definitely positive. In this latter case, the number and location (relative to the left ventricular wall position) of positive lesions will be recorded. Similarly, FDG-PET studies (performed as part of the inclusion criteria) will be reviewed and the number and location of FDG-avid lesions recorded.

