Primary Endpoint: Positive or abnormal OctreoScan or DOTATATE uptake in patients with cardiac sarcoidosis

Secondary Endpoint: Differences in OctreoScan uptake at 4 hours vs. 24 hours post-radiotracer injection

c. Statistical methods

Data Ascertainment and Analysis:

All statistical analysis will be done using SPSS (version 21.0). A P value <0.05 will be considered statistically significant for all calculations.

Qualitative assessment of OctreoScan or DOTATATE cardiac uptake: First, Cohen's kappa coefficient will be used to examine the visual inter-rater agreement between readers. We expect a kappa of at least 0.9 (excellent). Subsequently, the percentage of patients with abnormal OctreoScan or DOTATATE will be compared between patients with suspected sarcoidosis and those in a control group (Table 1, Figure 2) using chi2.

Semiquantitative assessment of OctreoScan or DOTATATE cardiac uptake: The heart-to-blood pool ratio is a unitless continuous variable. We will use paired t-test to compare within group OctreoScan uptake between early and delayed imaging, and independent-measures t test to compare OctreoScan or DOTATATE uptake between patients with suspected sarcoidosis and the control group.

We will also investigate whether delayed imaging may lead to improved lesion detection performance due to a higher/better target-to-background ratio compared to early imaging. We will employ chi2 to compare if percentage of patients with abnormal OctreoScan varies significantly both on a patient- and lesion-basis between early and delayed imaging in both study groups.

Evaluation of early vs. delay imaging: We will employ chi2 to compare if percentage of patients with abnormal OctreoScan varies significantly both on a patient- as well as lesion-basis between early and delayed imaging in both study groups.

Comparison with FDG-PET: We will also compare if foci of increased OctreoScan or DOTATATE uptake are similar in number and localization compared to FDG-PET scans.

Expected Results:

Our main hypothesis is that OctreoScan or DOTATATE uptake in the heart will be semiquantitatively (heart-to blood pool ratio will be ≥ 2.0) high enough to allow visualization of OctreoScan or DOTATATE activity in patients with cardiac sarcoidosis, compared to the control group, where myocardial uptake will be similar to blood pool activity (heart-to blood pool ratio of ~ 1.0).

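### Sub-Aim 1 compares 4 h and 24 h lesion detection by percentage abnormal alone, so at lesion level it cannot tell more FDG lesions found from more foci outside them

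*Combined protocol and SAP*

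**What the plan says.** Sub-Aim 1 (Specific Aims) is stated as follows: "To evaluate whether 4-hour (early) compared to 24-hour (delayed) post-OctreoScan injection imaging yields similar lesion detection performance". The Statistical methods section adds a direction: "We will also investigate whether delayed imaging may lead to improved lesion detection performance due to a higher/better target-to-background ratio compared to early imaging".

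The visual analysis for this question appears twice in Statistical methods, in nearly the same words. Under the early-versus-delayed heading, chi2 is used to "compare if percentage of patients with abnormal OctreoScan varies significantly both on a patient- as well as lesion-basis between early and delayed imaging". No reference standard, matching rule or lesion-level denominator is given. The general significance rule is "A P value <0.05 will be considered statistically significant for all calculations". The early and delayed heart-to-blood-pool ratios are also compared by paired t-test, but that measures uptake, not whether a lesion was found.

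The locations needed for a reference are collected. The OctreoScan image interpretation section records the number and left ventricular wall location of lesions on definitely positive reads, and both early and delayed sets are read. It also says "FDG-PET studies (performed as part of the inclusion criteria) will be reviewed and the number and location of FDG-avid lesions recorded". A separate paragraph in Statistical methods, serving Sub-Aim 2, compares foci with FDG-PET in number and location. It names no time point, test or matching rule.

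On numbers: "We expect imaging 10 patients with OctreoScan and 20 patients with DOTATATE". Only the OctreoScan patients have two time points.

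**The concern.** Detection performance has two parts: how many reference lesions are found, and how many calls fall where the reference shows nothing. A percentage abnormal adds the two together. At lesion level, a focus in an FDG-positive wall and a focus in an FDG-negative wall each add one to the count. A paired test would not cure this, because the outcome being paired would be the same.

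The protocol itself describes one route by which signal could appear away from a lesion. In its control series it attributes the higher inferior-wall and septal ratios mainly to "scatter emitted from the liver and spleen (Fig 2G) into the inferior wall", with a smaller effect on the septum. Nothing in the documents shows that such signal would be equal at 4 h and 24 h. The control series cannot supply that comparison, because it was imaged only at 24 h.

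At stake is the conclusion about imaging time. The protocol expects delayed imaging to do better, so a larger 24 h count would agree with the expectation whatever its source.

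**Working it through.** **No figure to reproduce.** The plan gives no sample size, power, detection rate or margin for Sub-Aim 1. What follows is an illustration.

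**Inputs from the documents.** 10 OctreoScan patients; four left ventricular walls (septum, lateral, anterior, inferior), so 10 × 4 = 40 walls per time point; significance at P < 0.05.

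**Assumptions.** Each patient has 1, 2 or 3 FDG-positive walls with equal chance (mean 2, so on average 20 FDG-positive and 20 FDG-negative walls). Detection in FDG-positive walls is 60% at both times. FDG-negative walls are called positive in 5% at 4 h and in 5%, 15% or 25% at 24 h. Walls are independent. The wall serves as the lesion-level unit, because the plan gives none.

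**Expected foci = 20 × detection + 20 × off-site rate.**
- 4 h: 20 × 0.60 + 20 × 0.05 = 12 + 1 = 13.
- 24 h at 25% off-site: 12 + 20 × 0.25 = 12 + 5 = 17.

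All four extra foci lie outside FDG lesions.

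**Simulated trials.** The chi2 columns give the share of trials significantly favouring 24 h.

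| Detection, 4 h / 24 h | Off-site, 4 h / 24 h | 24 h count higher | Wall-level chi2 |
|---|---|---|---|
| 60% / 60% | 5% / 5% | 44% | under 1% |
| 60% / 60% | 5% / 15% | 66% | about 4% |
| 60% / 60% | 5% / 25% | 82% | about 12% (8% with continuity correction) |
| 60% / 50% | 5% / 25% | about 65% | about 5% |

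The first row is below 50% because of ties: 100% − 2 × 44% = 12%.

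**The planned test at the mean result, 13/40 v 17/40.** chi2 = 80 × (13 × 23 − 17 × 27)² / (40 × 40 × 30 × 50) = 80 × 160² / 2,400,000 = 0.85, p = 0.36.

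**Patient level.** The chance that a patient with k FDG-positive walls is positive only off-site is 0.4^k × [1 − (1 − f)^(4−k)], where f is the off-site rate.
- f = 5%: (0.0571 + 0.0156 + 0.0032) / 3 = 2.5%.
- f = 25%: (0.2313 + 0.0700 + 0.0160) / 3 = 10.6%.

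The patient-level chi2 significantly favours 24 h in about 3% of trials in the 5% v 25% scenario.

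**Range under stronger assumptions.** With 70% detection at both times and a fixed 10, 20 or 30 of 40 walls FDG-positive, the wall-level chi2 significantly favours 24 h in 42%, 17% and 6% of runs at 5% v 30% off-site, and in 92%, 56% and 15% at 5% v 50%.

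**A constructed case shows that a significant reversal is possible.** Take 20 of 40 walls FDG-positive. At 4 h, 14 on-site + 1 off-site = 15; at 24 h, 12 + 13 = 25. Then chi2 = 80 × (15 × 15 − 25 × 25)² / 40⁴ = 5.0, p = 0.025 (0.044 with continuity correction), favouring 24 h. Matched to FDG, detection is 14/20 = 70% v 12/20 = 60%, and off-site calls are 1/20 = 5% v 13/20 = 65%. Here 24 h finds fewer FDG lesions and has more off-site foci. The case was chosen to show the mechanism, not its likelihood.

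**The case against.** The strongest reply is that nothing in the documents shows off-site foci to be common, or to differ between 4 h and 24 h. In the 24 h control series the myocardium could not be told apart visually from blood pool, and Table 1 gives an inferior-wall ratio of 1.03 (maximum 1.32). Study SPECT images are reconstructed with scatter and attenuation correction. Lesions are recorded only on definitely positive reads, which filters out weak spill-in. This stands: the off-site difference is an assumption, and the high significance rates above need off-site rates of 30-50%, mostly with few FDG-positive walls.

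Second, abnormal FDG uptake is an inclusion criterion, so the percentage of abnormal patients is already a crude detection rate against FDG. This also largely stands. A scan positive only in an FDG-negative wall still counts as abnormal, but the gap lies mainly at lesion level.

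Third, a comparison with FDG by location is planned. A reader might infer that the trial makes no such check, and that would be wrong. What is missing is its link to time point, and so to Sub-Aim 1.

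Fourth, the Background calls FDG-PET non-specific for cardiac sarcoidosis. An OctreoScan focus without an FDG counterpart is therefore discordant; the documents do not support calling it false.

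Finally, the declared secondary endpoint is the difference in uptake between the two times, which the paired t-test addresses. That is true, but Sub-Aim 1 and the Expected Results are worded in terms of detection.

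**Conclusion.** The point holds at lesion level and conditionally. The planned early-versus-delayed comparison cannot separate more FDG lesions detected from more foci outside them, and it can point the wrong way if off-site foci differ between time points.

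A reader might go further and infer that the trial would report 24 h as the better detector because of off-site foci. The documents do not support that. They give no off-site rate at either time. Under the assumed 60% detection and 5% v 25% off-site calls, the raw count favours 24 h in about 82% of trials (44% when nothing differs), but the planned kind of test is significant for 24 h in only about 8-12% at wall level. The likelier result is a non-significant difference whose direction cannot be interpreted.

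These figures rest on 10 patients, four independent walls each, and the wall as the lesion-level unit. The question is secondary and concerns about a third of a 30-patient pilot. I would class this as a cheap improvement.

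**What to change.** In Statistical methods, under the evaluation of early versus delayed imaging, add FDG-referenced wall-level results, for example:

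*At each time point, OctreoScan foci will be matched to the same patient's FDG map by left ventricular wall (septum, lateral, anterior, inferior). We will report separately the paired 24 h minus 4 h difference in (a) the proportion of FDG-positive walls detected and (b) the proportion of FDG-negative walls called positive, with intervals obtained by resampling patients. Positive calls in FDG-negative walls will be described as FDG-discordant. FDG is an imperfect reference.*

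The patient-level percentage can stay as a crude detection rate. No rule declaring one time point better is needed: with about 10 patients, (a) and (b) are best shown side by side, and such a rule would penalise lesions that FDG missed.

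Two details need settling. FDG locations must be coded on the same four walls, and the plan should say how borderline reads are scored, since locations are recorded only for definitely positive reads.

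The cost is SAP wording and a modest extra analysis, with no new scans or visits. The small downside is reliance on FDG as reference, which the text should state.

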c. Inclusion Criteria for participation in follow-up study with Dotatate

- Initial dotatate PET scan consistent with active sarcoidosis. Defined as focally increased radiotracer activity in at least one left ventricular wall.

- Being on corticosteroid therapy at a dose of ≥ 10 mg/day of oral prednisone or equivalent for at least 6 weeks since initial dotatate PET scan.

IV. SUBJECT ENROLLMENT

Recruitment Procedures: Potential subjects will be recruited from the following sources: 1) Cardiomyopathy clinic; (2) Sarcoidosis clinic and 2) Nuclear Cardiology Laboratory.

Screening procedures will include daily or weekly queries for potential eligible subjects from lists of patients who have either undergone nuclear imaging or are scheduled to undergo imaging procedures for sarcoidosis. [name] will plan on educating the Nuclear Medicine Department staff about the study (recruitment information) as an additional way to ensure potential eligible patients are referred to the study. Our Nuclear Medicine Department staff will be instructed to notify [name] if they encounter an abnormal FDG-PET suggestive of active cardiac sarcoidosis, so that the study can be introduced by the nuclear technologists, physiologists or physicians before they leave the Nuclear Medicine facility.

If potential candidate is identified in the sarcoidosis clinic and/or cardiomyopathy clinic, patient's doctor or clinic staff will introduce the study to the patient. If patient is interested in learning more about the study, [name] will be notified, who will further discuss the study with the patient after the conclusion of his/her appointment with patient's doctor.

If potential patient is identified in the Nuclear Cardiology Laboratory the day of the patient's FDG PET scan, patient will be approached by one of the nuclear technologists, physiologists or physicians before they leave the Nuclear Medicine facility. Only non-study staff members may approach a potential patient in this manner. They can determine whether or not a patient may be interested in finding out more information and can refer him or her to the study team as appropriate. In this setting, the patient may be an inpatient or outpatient.

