2. Semi-quantitative assessment of OctreoScan cardiac uptake: A heart to blood pool background ratio will be calculated using a circular region of interests (ROI) applied to each focus of increased radiotracer uptake visualized in the left ventricle on the transverse and/or coronal tomographic slice of the fused SPECT/CT images. A background ROI of the same size will be applied to the blood pool in the left ventricular cavity. In addition, the relative myocardial contrast will be assessed with measurement of myocardial uptake in ROIs positioned in: 1) interventricular septum 2) lateral wall 3) anterior wall and 4) inferior wall. ROI placement will be confirmed via image fusion with the CT portion from the SPECT/CT study (similar to Figure 2). This qualitative and semiquantitative approach will be performed in both early and delayed datasets by 2 separate nuclear medicine physicians.

Image Interpretation for DOTATATE:

DOTATATE uptake in the heart will be assessed both qualitative and semi-quantitatively.

1. Qualitative Assessment of OctreoScan cardiac uptake: Two board-certified nuclear medicine physicians will review the limited whole body and cardiac PET/CT images independently of each other and grade each image set based on DOTATATE uptake in the heart as: 1) negative, 2) borderline positive or 3) definitely positive. In this latter case, the number and location (relative to the left ventricular wall position) of positive lesions will be recorded.

2. Quantitative assessment of DOTATATE cardiac uptake: The axial PET image slice with maximum cardiac uptake will be selected. A standardized 15 mm circular region will be placed over each myocardial wall area with the peak activity. ROI placement will be confirmed via image fusion with the CT portion from the PET/CT study. Each ROI will be used to derive maximum (SUVmax) and mean standardized uptake values (SUVmean). A background ROI of the same size will be applied to the blood pool in the left ventricular cavity, and similarly, SUVmax and SUVmean will be derived to serve as reference. Then, signal-to-background ratios will be calculated.

This qualitative and semi-quantitative approach will be performed in both early and delayed datasets by 2 separate nuclear medicine physicians.

BIOSTATISTICAL ANALYSIS

a. Specific data variables being collected for the study

Please see excel attachments

b. Study endpoints

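### Aim 1 and the main hypothesis name a heart-to-blood-pool ratio of at least 2.0, but no planned analysis sets the ratio against 2.0

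*Combined protocol and SAP*

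**What the plan says.** Section II, Aim 1, asks whether patients show a "signal high enough (heart-to-blood pool ratio ≥ 2.0) to be visually detected compared to a control group of individuals", with controls expected near 1.0. Under Expected Results in the Biostatistical Analysis section, the main hypothesis repeats the figure: uptake will be "semiquantitatively (heart-to blood pool ratio will be ≥ 2.0) high enough to allow visualization".

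The primary endpoint (Biostatistical Analysis, b) is "Positive or abnormal OctreoScan or DOTATATE uptake in patients with cardiac sarcoidosis", with no ratio attached. Part c lists these analyses:

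- kappa for agreement between the two readers;
- chi-squared tests on the percentage of abnormal scans, against controls and for early against delayed imaging;
- a paired t test of early against delayed OctreoScan uptake;
- an "independent-measures t test to compare OctreoScan or DOTATATE uptake between patients with suspected sarcoidosis and the control group";
- a comparison of the number and location of foci with FDG-PET.

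Scans are classified by eye. In section V.d the readers "grade each image set based on OctreoScan uptake in the heart as: 1) negative, 2) borderline positive or 3) definitely positive", and DOTATATE scans are graded in the same way. Section III.c describes an active DOTATATE scan for follow-up without a ratio: "Defined as focally increased radiotracer activity in at least one left ventricular wall".

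For OctreoScan, the V.d ratio comes from a region "applied to each focus of increased radiotracer uptake visualized in the left ventricle". Four wall regions are an addition: "In addition, the relative myocardial contrast will be assessed with measurement of myocardial uptake in ROIs positioned in" the septum and the lateral, anterior and inferior walls. For DOTATATE, V.d derives both SUVmax and SUVmean for each wall region and then signal-to-background ratios.

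**The concern.** The one number attached to the patients' uptake in the main hypothesis has no analysis. The between-group t test has a null of no difference from controls, so it can reject when patients average well below 2.0. A reader of the results would have a p value for a weaker statement, but no interval set against 2.0 and no count of patients who reach it.

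Two details make the gap harder to close after the event. The plan does not say whether 2.0 applies to each patient or to the group mean. The text also does not reduce the several foci or walls, two readers, two OctreoScan time points and two SUV measures to one value per patient, and a patient with no visible OctreoScan focus has no focus ratio. If these choices are made once the data are known, they can move the result to either side of 2.0.

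**Working it through.** **Inputs from the documents.** Control mean 0.94, SD 0.17, 15 OctreoScan patients (section I.c and Table 1); 10 OctreoScan and 20 DOTATATE patients expected (V.a); significance at p<0.05 (Biostatistical Analysis, c).

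**Assumptions.** Two-sided tests. Patient SD from 0.17 to 1.0, because none is given. OctreoScan control values are taken to hold for DOTATATE. Both Student and Welch are shown, because the plan names neither.

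**Reproducing the control figures.** The wall means average (1.02 + 1.03 + 0.92 + 0.81)/4 = 0.945, in line with 0.94. Pooling the 60 wall values:

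- within walls: 14 × (0.15² + 0.13² + 0.15² + 0.15²) = 1.182;
- between walls: 15 × Σ(wall mean − 0.945)² = 0.4755;
- SD = √[(1.182 + 0.4755)/59] = 0.168.

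So 0.17 appears to be a wall-level SD. The SD of a patient's four-wall mean cannot exceed the average of the wall SDs, (0.15 + 0.13 + 0.15 + 0.15)/4 = 0.145. Both values are carried forward as s0.

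**Smallest significant patient mean**, with n patients of SD s1:

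- Student: 0.94 + t(0.975, n+13) × sp × √(1/15 + 1/n), where sp² = [14·s0² + (n−1)·s1²]/(n+13).
- Welch: 0.94 + t(0.975, df) × √(s0²/15 + s1²/n), with Satterthwaite df.

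Low end, n=10, s0=0.145, s1=0.17, Student: sp = √[(0.29435 + 0.2601)/23] = 0.1553; SE = 0.1553 × 0.4082 = 0.0634; 0.94 + 2.069 × 0.0634 = 1.07.

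High end, n=10, s0=0.17, s1=1.0, Welch: SE = √(0.001927 + 0.1) = 0.3193; df = 9.35; 0.94 + 2.249 × 0.3193 = 1.66.

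Ranges across both tests and both control SDs:

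| Assumed patient SD | n=10 | n=20 |
|---|---|---|
| 0.17 | 1.07 to 1.09 | 1.05 to 1.06 |
| 0.3 | 1.12 to 1.17 | 1.10 to 1.12 |
| 0.6 | 1.27 to 1.37 | 1.23 to 1.27 |
| 1.0 | 1.48 to 1.66 | 1.41 to 1.47 |

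Replacing 0.17 by 0.145 lowers a cut-off by at most about 0.013. The cut-off reaches 2.0 only at a patient SD of about 1.48 (Welch) or 2.0 (Student) for n=10, and about 2.0 (Student) or 2.26 (Welch) for n=20.

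**Worked example: observed mean 1.4, SD 0.6, difference from controls 0.46.**

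- n=10: p = 0.0086 to 0.0095 (Student) or 0.039 to 0.040 (Welch). 95% CI for the mean: 1.4 ± 2.262 × 0.6/√10 = 0.97 to 1.83.
- n=20: p = 0.0067 to 0.0070 (Student) or 0.0033 to 0.0035 (Welch). 95% CI: 1.4 ± 2.093 × 0.6/√20 = 1.12 to 1.68.

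Every p value is below 0.05, and both intervals exclude 2.0.

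**The case against.** In both places 2.0 sits in a parenthesis that explains how strong a signal must be to be seen, and the hypothesis appears under Expected Results. The control ratio near 1.0 and the kappa of at least 0.9 are also expectations with no test against them. On that reading the real claim is visual detection compared with controls, which the visual endpoint, two-reader grading and chi-squared test address. This is a single-center pilot, and the ratio is not its primary endpoint. Much of this stands. It lowers the weight of the point, but Aim 1 and the main hypothesis still both carry the figure.

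Three stronger inferences are tempting and are not supported:

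- **That the plan would present a significant t test as proof of 2.0.** It says nothing of the kind.
- **That a shortfall would be concealed.** The group mean would stand beside the t test, so a low mean would be visible. What is missing is an interval against 2.0 and a count.
- **That the patient-level ratio is left wholly open.** The data variables are listed in attachments that were not available and may settle some choices. The text also narrows some: four walls are measured as well as foci, the controls were imaged at 24 hours, and DOTATATE regions are placed on the slice of maximum uptake. None of this fixes one value per patient in the text.

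It is also fair that the size rests on an assumed patient SD. In addition, the control figure averages four walls while the OctreoScan patient ratio is per visible focus, so the modelled comparison may not be like for like. The logical gap needs none of these numbers.

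**Conclusion.** The point holds in a limited form. As written, the plan can address whether uptake is visible and whether it differs from controls, but it has no analysis for the 2.0 part of its own aim and hypothesis. Significance against controls would not supply one: over the assumed patient SDs of 0.17 to 1.0 it arises from observed means of about 1.07 to 1.66 (n=10) or 1.05 to 1.47 (n=20). Those ranges depend on the assumed patient SD, on two-sided testing and, for n=20, on carrying OctreoScan control values over to DOTATATE. At a much larger patient SD, about 1.5 or more with 10 patients, the cut-off can reach 2.0, so the arithmetic is not universal. The weight lies between a minor point and one that should be fixed: a cheap improvement in a pilot, with no bearing on the visual primary endpoint.

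**What to change.** Before analysis, and consistently with the variable attachments:

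1. Fix one ratio per patient for each tracer. For OctreoScan, state which focus, which time point, how the two readers are combined, and how a patient with no visible focus is counted. For DOTATATE, state which wall, SUVmax or SUVmean, and how the readers are combined.
2. State whether 2.0 applies to each patient or to the mean.
3. Report by tracer, over all patients imaged with it, the number and proportion at or above 2.0 with an exact 95% CI, and the mean ratio with its 95% CI set against 2.0.
4. Keep the t test against controls as supportive.
5. If 2.0 is only an expectation, say so and still give these summaries. A pilot needs no pass/fail rule.

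The cost is a short specification: the ratios are already to be calculated, so no patients, scans or visits are added. The downside is that the result may look less favourable than a difference from controls, and the exact intervals are wide: 8 of 10 gives 44% to 97%, and 16 of 20 gives 56% to 94%.
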